## 11.2.2 Secondary Effectiveness Endpoints

One of the secondary objectives of the study is to show that 6-weeks after treatment the Active Treatment group has a similar amount of pain relief as the Sham Treatment group. Change in WOMAC Pain from the Baseline visit to the six-week visit will be calculated for each subject as:

Change in WOMAC Pain =

6-Week Visit WOMAC Pain – Baseline Visit WOMAC Pain

such that a negative value indicates a decrease in the WOMAC Pain, while a positive value indicates the opposite.

The difference in the average Change in WOMAC Pain between the two treatment groups will be calculated as Active Change in WOMAC Pain average - Sham Change in WOMAC Pain average, such that a positive difference indicates that the Active Treatment Group had a larger average Change in WOMAC Pain than the Sham Treatment group, while a negative value indicates the opposite. Since a negative Change in WOMAC Pain is indicative of pain relief, then a negative difference between treatment groups reflects a positive outcome for the study.

A non-inferiority hypothesis test using the two-independent sample t-test will be used to statistically evaluate the difference in the mean Change in WOMAC Pain between the two treatment groups. A confidence interval for the difference in the average Change in WOMAC Pain between the two treatment groups will be provided to assist in the interpretation of the results.

The objective of this secondary endpoint is to show that the average reduction in WOMAC Pain for the Active Treatment group is not worse than the average reduction for the Sham Treatment group by more than one-half of the common standard deviation for the Change in WOMAC Pain scores. The objective is met when the resulting t-test is statistically significant using a one-sided  $\alpha = 0.025$  level of statistical significance.

A variety of additional secondary effectiveness endpoints will be assessed to further characterize pain relief, functional performance, and range of motion. These include:

- Active Range of Motion
- 40 Meter Walk Test
- 30 Second Chair Test
- Length of Hospital Stay
- WOMAC Scores (Pain, Stiffness, and Function)
- SF-36 Scales and Summary Measures
- PROMIS-29 Profile Domains and Pain Intensity Score
- NRS for Pain

For each secondary effectiveness endpoint, the result, as well as the Change from Baseline value, will be summarized at each visit the endpoint is collected. Two sets of hypotheses tests will be performed: the paired t-test will be used to evaluate if the Change from Baseline result is statistically different from no change, while the two-independent sample t-test will be used to statistically evaluate the difference between the two treatment groups for both the original result and for the Change from Baseline result. Confidence intervals will be provided to assist in the interpretation of the results.

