#### 10.7 **Study Follow Up**

Study-related follow-up visits occur at the investigational site at Week 2, Week 4, Week 6, and Week 12. The study's schedule of assessments is shown in Table 3.

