# 10.7.1 Visit 4/2 Weeks Post-op (14 ±3 Days), Visit 5/4 Weeks Post-op (28 ±5 Days), and Visit 6/6 Weeks *Post-op (42 ±5 Days)*

Subjects will be evaluated and data collected per the schedule of events. Any changes in concomitant medications/concurrent procedures will be documented. Any anticipated observations, adverse events, adverse device effects and/or SAE/UADE/USADE will be assessed and documented. Photographs may be taken of the treatment area.

The Subject will complete a WOMAC questionnaire, NRS for Pain when standing from a seated position, PROMIS questionnaire, and SF-36 questionnaire. Subjects will be asked to assess their treatment assignment (the blind).

Subjects will answer Satisfaction questions at Visit 6.

The subject will complete the Physical Performance Measures in the following order under supervision of the investigator or designee:

- Active Range of Motion
- 40 Meter Walk Test
- 30 Second Chair Test

Detailed instructions for the conduct of these performance measures are included in the Study Operations Manual. Assistive/ambulatory device usage and work status will also be assessed.

Utilization of healthcare services post-discharge, or since the previous follow-up visit, will be assessed. Subjects will be asked to report any Secondary Surgical Interventions, Emergency/Urgent care visits, Unscheduled physician office visits, and other healthcare services used since their last study visit. Investigators will also record any additional or unscheduled services performed at follow-up visits (examples include knee aspiration, unscheduled x-ray, other unscheduled diagnostic procedures, etc.).

Subjects will be asked to bring all prescription opioid bottles to all study follow-up visits. A pill count will be completed by the study coordinator, or designee, and opioid medication will be redispensed to subjects.

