# 11.3.5 Cohort for Secondary Endpoint

The Secondary Endpoint, Change in WOMAC Pain, will be made using the Per-Protocol Cohort. Analyses for all other secondary endpoints will be repeated using the Safety/ITT Cohort and the Per-Protocol Cohort

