#### 11.5 **Handling of Dropouts or Missing Data**

All endpoints will be analyzed "as-is" without any special data imputation methods used to replace missing data. Consequently, subjects missing results for a specific analysis will be excluded from that analyses.

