# 11.9 Sensitivity Analyses

No imputations for missing data will be made for the Primary and Secondary Effectiveness Endpoints. All patients enrolled and randomized in the study will be included in all analyses. Sensitivity analyses may be considered and will be described in the final Statistical Analysis Plan for the study. Nevertheless, the totality of the results will be used when evaluating overall Study Success.

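### Secondary endpoints measured at four post-operative visits are compared by available-case t-tests at each visit, which biases the comparison if missed visits depend on recovery and missingness differs by arm

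*Protocol*

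**What the plan says.** Protocol section 10.7 sets the visits: "Study-related follow-up visits occur at the investigational site at Week 2, Week 4, Week 6, and Week 12". Section 10.7.1 lists what is collected at Weeks 2, 4 and 6: "The Subject will complete a WOMAC questionnaire, NRS for Pain when standing from a seated position, PROMIS questionnaire, and SF-36 questionnaire", followed by range of motion, the walk test and the chair test. Section 10.7.2 repeats the set at Week 12, and section 10.3 collects it at baseline.

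The last paragraph of section 11.2.2 says that each secondary endpoint "will be summarized at each visit the endpoint is collected", and that "the two-independent sample t-test will be used to statistically evaluate the difference between the two treatment groups for both the original result"; change scores are tested in the same way. Section 11.5 analyses all endpoints "without any special data imputation methods used to replace missing data", so that "subjects missing results for a specific analysis will be excluded from that analyses".

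On cohorts, section 11.3.5 places the change in WOMAC Pain on the Per-Protocol Cohort. For the rest it says: "Analyses for all other secondary endpoints will be repeated using the Safety/ITT Cohort" and the Per-Protocol Cohort. Section 11.9 adds: "All patients enrolled and randomized in the study will be included in all analyses". The only model named anywhere is the two-way analysis of variance for poolability in section 11.6.

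**The concern.** Taken together, sections 11.2.2 and 11.5 give a series of available-case comparisons, each on whoever has a value at that visit. A subject who recovered poorly at Week 4 and then missed Week 6 drops out of the Week 6 comparison, even though the Week 2, Week 4 and perhaps Week 12 values say a good deal about the missing one. Attendance at on-site visits after knee replacement could plausibly depend on how recovery is going. If it does, and if the arms lose different proportions of subjects or lose them by different mechanisms, the two groups compared at that visit are no longer those created by randomization.

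At stake are the results on pain, function and quality of life that support the trial's aim of lowering opioid use without loss of pain relief (section 11.1). The point concerns missed visits only. It does not concern subjects who attend but cannot perform a test, Length of Hospital Stay (measured once), or the primary endpoint.

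**Working it through.** **Inputs from the protocol (section 11.10).** SD 22 for the change in WOMAC Pain, non-inferiority margin 11, one-sided alpha 0.025, 80% power, 64 analyzable per arm, 75 randomized per arm, and up to 10% without data. WOMAC Pain serves as the scale because it is the only repeatedly measured secondary endpoint with a stated SD.

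**Assumptions, not in the protocol.** Correlation between visits 0.5 to 0.7 for the bias and 0.3 to 0.7 for precision. Week 6 missed according to a logistic model in the standardized Week 4 score, slope 0.5 to 1.5 per SD, with worse scores missed more often. No true difference between arms.

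**1. The plan's own figure.** n = 2(1.960 + 0.842)²(22/11)² = 62.8, so 63 per arm by the normal approximation. The noncentral t gives 64, as stated. No number in the protocol is wrong here.

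**2. Bias of the available-case difference.** With Z the standardized Week 4 score, P(miss) = 1/(1 + exp(−(a + bZ))), where a is set to give the required missing rate. An arm's Week 6 mean among attenders is then shifted by ρ × 22 × E[Z | attended], and the bias is the difference of the two shifts.

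| Slope b | E[Z \| attended], 5% missing | 15% missing | Difference | Bias, ρ = 0.5 | Bias, ρ = 0.7 |
|---|---|---|---|---|---|
| 0.5 | −0.025 | −0.073 | 0.048 | 0.53 | 0.74 |
| 1.0 | −0.047 | −0.133 | 0.0855 | 0.94 | 1.32 |
| 1.5 | −0.065 | −0.175 | 0.110 | 1.21 | 1.70 |

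For example, 22 × 0.7 × 0.0855 = 1.32.

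- At 12% versus 8% the differences in E[Z | attended] are 0.019, 0.034 and 0.044, giving biases of 0.21 to 0.68 points.
- At 10% in both arms with the same slope the two shifts cancel and the bias is 0.
- The arm that loses more subjects looks better, so the bias favours the device if that is the active arm and counts against it if that is sham.
- The standard error at 15% versus 5% is 22 × √(1/63.75 + 1/71.25) = 3.79.
- In simulated trials at 15% versus 5% (6,000 per setting), a likelihood estimate using the Week 4 value had a bias of at most 0.1 point.

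**3. Precision at 10% missing.** The t-test uses 75 × 0.9 = 67.5 per arm. With Weeks 2, 4 and 12 observed and equal correlation ρ, R² = 3ρ²/(1 + 2ρ) and the effective n is 75/[(1 − R²)/0.9 + R²]. Power is Φ(11/(22√(2/n)) − 1.96).

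| Analysis | R² | Effective n per arm | Power |
|---|---|---|---|
| t-test on available cases | – | 67.5 | 82.8% |
| Repeated measures, ρ = 0.3 | 0.169 | 68.7 | 83.4% |
| Repeated measures, ρ = 0.5 | 0.375 | 70.1 | 84.2% |
| Repeated measures, ρ = 0.7 | 0.613 | 71.9 | 85.0% |

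The gain is about 0.6 to 2.2 power points. At 20% missing it is about 1.4 to 5.0 (78.2% against 79.6% to 83.2%).

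**4. Sections 11.5 and 11.9 side by side.** Section 11.5 excludes a subject from any analysis whose result is missing; section 11.9 puts every randomized subject in every analysis. Without imputation, and with one t-test per visit, both cannot hold.

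**The case against.** Visit-by-visit t-tests are a conventional choice for endpoints meant to characterize an outcome, and section 11.9 lets the statistical analysis plan add sensitivity analyses. The trial is sham-controlled with blinded subjects, so nothing in the protocol points to a three-fold imbalance in attendance. The bias is small against an SD of 22, and 67.5 per arm still exceeds the required 64. Section 11.2.2 also does not say in so many words that each visit gets its own test. All of this stands and limits the weight of the point. It does not remove it: the protocol itself fixes the test and the exclusion rule, testing at each visit is the plain reading of section 11.2.2, and sensitivity analyses are only optional.

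Three stronger readings are tempting, and the document does not support them.

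- **That the t-test is biased whenever attendance depends on recovery.** With the same rate and mechanism in both arms the shifts cancel.
- **That the type I error rises well above a nominal one-sided 0.025.** Biases of 0.53 to 1.70 points are 0.14 to 0.45 standard errors. Φ(−1.96 + 0.14) and Φ(−1.96 + 0.45) give about 0.034 to 0.065 if the imbalance favours the device, but the reverse imbalance gives about 0.018 down to 0.008. Moreover, among the repeatedly measured secondary endpoints that threshold is stated only for the Week 6 WOMAC Pain non-inferiority test, not for the tests discussed here.
- **That a repeated-measures model would repair that non-inferiority test.** Sections 11.3.3 and 11.3.5 restrict it to subjects who completed the 6-week visit, so nobody who missed Week 6 can enter it.

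**Conclusion.** The point holds as a cheap improvement to the secondary analyses, not as an error in a stated figure. The planned comparisons discard recorded information and are open to bias when missed visits depend on earlier recovery and missingness differs by arm. The size is modest: about 0.5 to 1.7 points at 15% versus 5% missing, 0.2 to 0.7 at 12% versus 8%, and about zero when the arms match, against a standard error of about 3.8. These figures rest on the assumed correlations, slopes and missing rates, and the direction cannot be known in advance. The loss of precision alone, at the 10% that the protocol allows for, would not justify a change. The conflict between sections 11.5 and 11.9 needs resolving in any case.

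**What to change.** - **Section 11.2.2.** For the secondary endpoints analysed in the Safety/ITT Cohort and measured at several visits (so not Length of Hospital Stay), make the between-group comparison one mixed model for repeated measures per endpoint. Include treatment, visit, treatment-by-visit, baseline-by-visit and site, with an unstructured covariance. Fit it to all randomized subjects with at least one post-operative value, report the treatment contrast at each visit, and keep the t-tests as supportive.
- **Section 11.5.** State that a missed visit removes only that visit's value from the model, not the subject.
- **Section 11.9.** Reconcile it with section 11.5. Even the model cannot use a subject with no post-operative value, so the statement about including everyone needs rewording.
- **Week 6 WOMAC Pain non-inferiority test.** Leave it on the Per-Protocol Cohort under sections 11.3.3 and 11.3.5. The same model in all randomized subjects can be reported beside it as a sensitivity analysis.

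The cost is wording and slightly more programming, with no new data or subjects. Nothing is imputed, so that rule in sections 11.5 and 11.9 is kept. The downside is reliance on data being missing at random, a weaker assumption than the available-case t-tests generally need.

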# **Protocol Synopsis**

Title	A Post-Market, Multi-Center, Prospective, Double-blind, Randomized, Controlled Study to Evaluate the iovera° Device in Treating Pain Associated with Total Knee Arthroplasty				
Study Device	iovera° (myoscience Inc., Fremont, CA)				
Study Objective	To evaluate the outcomes of patients undergoing iovera° treatment of the ISN and AFCN prior to total knee arthroplasty to provide temporary postoperative pain relief				
Study Design	Multi-center, prospective, randomized				
Treatment Groups	Pre-operative iovera° treatment vs. pre-operative sham iovera° treatment				
Duration of Participation	Up to 16 weeks (12 weeks post-op)				
Study Population	Male or female, ages 22 to 79 scheduled to undergo a total knee replacement as a result of osteoarthritis				
Total Number of Subjects	150 subjects				
Number of Sites	Up to 8 sites				
Study Procedures	iovera° treatment introducing temporary nerve conduction block of the ISN and AFCN				
Data Collection Tools	
 
WOMAC
 
SF-36
 
PROMIS
 
NRS for Pain
 
				
Primary Endpoint	Cumulative Opioid Consumption at 6 weeks post-TKA Surgery				
Secondary Endpoints	
 
Length of Hospital Stay
 
WOMAC Pain
 
WOMAC Function
 
Physical Performance (Measured by: Range of Motion, 30 Second Chair Test and 40 Meter Walk Test)
 
				

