#### 11. STATISTICAL METHODOLOGY AND ANALYSES

#### 11.1 Introduction

This is a prospective, randomized, sham-controlled, multi-center, post-market trial to evaluate the iovera° device in treating pain associated with total knee arthroplasty (TKA). The study is designed to investigate whether iovera° treatment prior to TKA decreases cumulative patient opioid use over the course of 6 weeks following TKA while maintaining similar levels of pain relief.

The study will also investigate whether there is a relationship between patients treated with iovera° and length of hospital stay; patient reported pain and function as measured by WOMAC; patient satisfaction; and improved physical rehabilitation as measured by functional performance measures and range of motion.

The primary safety endpoint is the onset of device-related adverse events through twelve-weeks after TKA surgery. The primary measure of effectiveness is the Total Daily Morphine Equivalent (TME) of pain medications used from Day of Discharge to the 6-week follow-up visit. In addition. Change from Baseline in WOMAC Pain at the 6-week follow-up visit will be evaluated as a secondary endpoint. A variety of secondary effectiveness endpoints, including performance and pain assessments, will be measured.

Up to 8 study sites within the United States will screen a sufficient number of subjects to ensure that 150 subjects (Randomized 1:1 to approximate 75 Active Treatment subjects plus 75 Sham Treatment subjects) will be randomized and treated.

Subjects will be randomized either to receive therapeutic treatment with the iovera° treatment or to receive a sham treatment with the iovera° treatment, using a balanced 1:1 active-to-sham randomization stratified by Study Site.

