# 11.4 Statistical Methods

## 11.4.1 General

Categorical data will be summarized using frequency tables, presenting the subject counts and relative percentages. McNemar's chi-square may be used to assess within-subject changes in a bivariate response variable.

Continuous variables will be summarized by the mean, standard deviation, median, minimum and maximum. Within-subject changes will be analyzed parametrically using the paired t-test if the differences are normally distributed, or non-parametrically using the sign-rank test if the differences are not normally distributed.

The SAS system or equivalent statistical package will be used to perform all analyses.

Exact confidence intervals will be generated for estimates of proportions. Asymptotic confidence intervals will be generated for estimates of means. Except where otherwise noted, the p-values of all tests will be reported without any correction for the multiplicity of tests performed.

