# 11.4.2 Derived Data – Change from Baseline Parameters

Within-subject change-from-baseline (pre-treatment baseline) values for a parameter are calculated as:

Change-from-Baseline = Follow-Up value – Pre-Treatment value

such that a positive value indicates an increase from the pre-treatment value to the follow-up value, whereas a negative result indicates the opposite.

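### Apart from 6-week change in WOMAC Pain, each additional secondary endpoint with a baseline is tested between groups both as visit value and as change from baseline, and neither is named as the result

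*Protocol*

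**What the plan says.** The Protocol Synopsis lists the secondary endpoints once each, by measure: hospital stay, WOMAC Pain, WOMAC Function and "Physical Performance (Measured by: Range of Motion, 30 Second Chair Test and 40 Meter Walk Test". Section 11.2.2 gives a longer list, introduced by "A variety of additional secondary effectiveness endpoints will be assessed to further characterize pain relief, functional performance, and range of motion". That list carries no metric, time point or success criterion.

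The analysis paragraph that closes section 11.2.2 covers all of them: "For each secondary effectiveness endpoint, the result, as well as the Change from Baseline value, will be summarized at each visit the endpoint is collected". It plans paired t-tests within groups and, between groups, a two-sample t-test to "statistically evaluate the difference between the two treatment groups for both the original result and for the Change from Baseline result". Section 11.4.2 defines the second version as "Change-from-Baseline = Follow-Up value – Pre-Treatment value". Section 11.4.1 adds that, unless noted otherwise, "the p-values of all tests will be reported without any correction for the multiplicity of tests performed". Nothing is noted otherwise for these endpoints.

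One secondary endpoint is treated differently. Section 11.1 says that "Change from Baseline in WOMAC Pain at the 6-week follow-up visit will be evaluated as a secondary endpoint", and section 11.2.2 gives its decision rule: "A non-inferiority hypothesis test using the two-independent sample t-test will be used to statistically evaluate the difference in the mean Change in WOMAC Pain". Section 11.10 sets its margin at 11 and its level at one-sided 0.025.

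**The concern.** The value at a visit and the change from baseline to that visit are not two outcomes. In a randomized trial the groups have the same expected baseline, so the between-group difference has the same expectation on either scale. The two tests differ only in how they treat a chance baseline imbalance: the first ignores it, and the second subtracts it in full.

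Two things follow. First, a reader who sees a significant p-value for one version of, say, the walk test and a non-significant one for the other has no rule for which one answers the question. The choice can then be made after the data are seen. Second, with a baseline correlation between 0 and 1 and similar SDs at both times, a model that estimates the baseline slope is more precise than either planned test. The plan therefore pays for an ambiguity and also loses power.

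**Working it through.** **The plan's own figure.** The additional endpoints have no stated effect size or sample size. The one secondary endpoint of this type with a fixed metric, 6-week change in WOMAC Pain, is stated to need 64 per group (section 11.10: SD 22, margin 11, 80% power, one-sided 0.025). The normal approximation gives 2 × 22² × (1.960 + 0.842)² / 11² ≈ 62.8, so 63; the t-based calculation gives 63.8, so 64. The stated figure reproduces.

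**Inputs.**
- From section 11.10: 150 randomized and up to 10% lost, so 150 × 0.9 = 135, or about 67 per arm.
- Assumed, because the protocol gives no figure: two-sided 0.05 per test, equal SDs at baseline and follow-up, correlation ρ between them of 0.3, 0.5 or 0.7, and a range of effects δ in SD units.

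**How closely the two tests agree.** With baseline X, follow-up Y and common variance σ², Cov(Y, Y − X) = σ²(1 − ρ) and Var(Y − X) = 2σ²(1 − ρ). The two test statistics therefore correlate at √((1 − ρ)/2), which is 0.592, 0.500 and 0.387 for the three values of ρ.

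**No treatment effect.** From the bivariate normal distribution, P(at least one significant) is 0.088, 0.091 and 0.094. Since P(both) = 0.10 − P(either), P(disagree) = 2 × P(either) − 0.10, which is about 0.076, 0.082 and 0.087. Simulated t-tests with 67 per arm agree closely. The two point estimates differ in sign with probability 0.30 to 0.37.

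**Power at δ = 0.4.** The standardized effect for the visit value is 0.4 × √(67/2) = 2.315. For the change it is divided by √(2(1 − ρ)), and for the baseline-adjusted model by √(1 − ρ²).

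| ρ | Value | Change | Adjusted | Simulated power: value / change / adjusted |
|---|---|---|---|---|
| 0.3 | 2.315 | 2.315/1.183 = 1.957 | 2.315/0.954 = 2.427 | 63% / 49% / 67% |
| 0.5 | 2.315 | 2.315/1.000 = 2.315 | 2.315/0.866 = 2.673 | 63% / 63% / 75% |
| 0.7 | 2.315 | 2.315/0.775 = 2.989 | 2.315/0.714 = 3.242 | 63% / 84–85% / 89% |

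The adjusted model in the simulation contains treatment and baseline; site was not simulated.

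**Disagreement on significance by effect size** (20,000 simulated trials per setting, range over ρ = 0.3 to 0.7):

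| True effect (SD) | Trials in which only one version is significant |
|---|---|
| 0 | 8–9% |
| 0.2 | 20–31% |
| 0.3 | 29–40% |
| 0.4 | 31–34% |
| 0.5 | 18–26% |
| 0.6 | 7–16% |
| 0.8 | 0.4–3% |

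Two significant results in opposite directions occurred in at most 1 of 20,000 trials in any setting.

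**The case against.** **The endpoints are supportive.** They are there to characterize the effect further, and they carry no alpha and no success rule. Section 11.3.4 rests success on the primary endpoint. Section 11.9 speaks of the totality of results but gives no rule that uses these tests. The protocol commits to performing both tests with confidence intervals, and it says openly that p-values are uncorrected. All of this stands, and it limits the consequence to how secondary results are read. Selective reporting is possible under the text, but the text does not announce it.

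**An SAP could name the metric.** It could. But the protocol is not silent here: it prescribes both between-group tests, so an SAP could settle the matter only by demoting one that the protocol fixes.

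**The 5% to 9% inflation is small** beside four follow-up visits, many scales and two analysis cohorts. That is true. What distinguishes this part is that both tests address one quantity, so the extra test adds no information that a single adjusted analysis would not give.

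**Stronger readings that the document does not support:**
- A reader might infer that no secondary endpoint has a rule. That is wrong for WOMAC Pain at 6 weeks. It reappears in the additional list, but its deciding analysis is stated.
- A reader might infer that one endpoint can give two contradictory findings. In practice the conflict is one p-value below 0.05 and one above, or, mainly when there is little or no effect, estimates of different sign.
- A reader might infer that the versions disagree in a third of trials whenever there is an effect. That figure belongs to effects near 0.4 SD; over the effects tabulated, the range is under 1% to 40%.
- A reader might infer that a change score over-corrects unless the correlation is 1. That holds only with equal SDs. In general the condition is that the slope of follow-up on baseline (correlation times SD ratio) equals 1.

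**Conclusion.** The point holds for the additional secondary endpoints with a baseline: range of motion, walk test, chair test, WOMAC scores other than the 6-week change in Pain, SF-36, PROMIS-29 and NRS. For each, section 11.2.2 fixes two between-group tests of the same treatment difference and designates neither. The ambiguity is in the text and needs no assumption.

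Its size does rest on the assumptions listed above. A false-positive chance of about 9% replaces 5% for one endpoint at one visit, and the effect sizes at which the two versions most often conflict are moderate ones. At 0.4 SD a single adjusted model has higher power than either planned test at all three correlations.

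The study success decision, the 6-week WOMAC Pain non-inferiority test and Length of Hospital Stay (which has no baseline) are untouched. This should be changed, but it is not critical.

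**What to change.** In section 11.2.2, for the additional endpoints with a baseline, replace the two between-group tests at each visit with one result: the treatment difference in the follow-up value, with its confidence interval, from a linear model with treatment, the endpoint's screening value and site. Keep visit values and changes from baseline as descriptive summaries without between-group p-values. State that the 6-week WOMAC Pain non-inferiority test and Length of Hospital Stay are outside this change.

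Naming either existing version would also remove the ambiguity. The adjusted model is preferable because it gains power at no cost in data: sections 10.3 and 10.7 (Table 3) already collect these measures at screening, and section 10.4 stratifies randomization by site.

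The cost is one paragraph of wording. The small downside is that subjects without a screening value do not enter the model; they could not enter the change test either. The change does not reduce the number of visits or cohorts reported, which is a separate matter.
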